14.3 FOLLOW-UP FOR PATIENTS AFTER DIAGNOSIS OF CIRRHOSIS

Following ELF or clinical diagnosis of cirrhosis, an authorised member of the research team at site should complete a Cirrhosis CRF and ensure that this is forwarded by fax to the CTRU within 7 days of diagnosis.

Subsequent to diagnosis, patients should attend an initial follow-up assessment at 3 months post diagnosis. All subsequent follow-up visits

should take place every 6 months. , Assessments to be performed are listed in Table 5 (over page). As per the pre-cirrhosis follow up visits a variation of plus or minus one month around the visit due date is permitted.

It is important to note that an individual patient may experience multiple episodes of liver related complications such as bacterial peritonitis, variceal haemorrhage or encephalopathy. Following on from a liver related complication, follow-up should continue on a 6-monthly schedule. If however, patients undergo liver transplantation, further 6 monthly follow-up will cease.

Table 5. Assessments to be performed at Follow-up for patients diagnosed with cirrhosis.

X = compulsory, **Z** = none of these tests are required as part of the ELUCIDATE protocol but if tests are performed as part of routine care please record findings and date of test. **R** = following *confirmed* clinical diagnosis of cirrhosis (according to clinical/biochemical/imaging criteria) patients randomised to the Routine Clinical Monitoring only arm should also have a single ELF test performed as soon after clinical diagnosis is confirmed and has been recorded in patient’s notes. Patients should be requested to refrain from eating a large meal in the 2 hours prior to providing the sample. (Please see section 10.1).

Assessment	Months from diagnosis of cirrhosis					
	0	3	9	15	21	27
History	X	X	X	X	X	X
Exam	X	X	X	X	X	X
ELF	R					
EQ-5D™/SF12v2™ and Health Usage Questionnaire	X	X	X	X	X	X
LFTs	X	X	X	X	X	X
FBC	X	X	X	X	X	X
INR	X	X	X	X	X	X
Glucose	X					
HOMA-IR	Z					
Liver biopsy	Z	Z	Z	Z	Z	Z
Fibroscan	Z		Z		Z	
AFP, USS, CT, MRI, OGD	SEE SECTION 14.3.1					

14.3.1 Compulsory scheduled assessments for the management of liver related complications.

OGD Timing

Timing of initial oesophagogastroduodenoscopy (OGD) following a diagnosis of cirrhosis:

- If the patient underwent OGD within 18 months prior to being diagnosed as cirrhotic, the next OGD should be performed **within 18 months of the previous OGD** unless clinically indicated sooner.
- If the patient did not have an OGD within 18 months prior to being diagnosed as cirrhotic, they should undergo OGD screening for oesophageal varices **within 3 months** of diagnosis of cirrhosis.

Timing of subsequent OGDs after a diagnosis of cirrhosis:

- If the previous OGD did not identify oesophageal varices, subsequent OGDs should be repeated **every 18 months from the previous OGD.**
- If small oesophageal varices at OGD are identified, OGDs should be repeated **every 6 months** to look for variceal progression.
- For large oesophageal varices currently being treated, the timing of subsequent OGDs can be dictated by local guidance.

Ultrasound scans/CT scan and AFP timing

Timing of initial scan following a diagnosis of cirrhosis:

- If the patient underwent an USS within 6 months prior to being diagnosed as cirrhotic, the next USS should be performed **within 6 months of the previous scan** unless clinically indicated sooner.
- If the patient did not have an USS within 6 months prior to being diagnosed as cirrhotic, they should undergo USS as screening for HCC **within 3 months** of diagnosis of cirrhosis.

Timing of subsequent scans after a diagnosis of cirrhosis:

- If the previous USS did not identify any lesions and the patient's AFP level remains stable, subsequent scans should be repeated **every 6 months from the timing of the previous scan.**

Timing of initial AFP test following a diagnosis of cirrhosis:

- If the patient had an AFP test within 6 months prior to being diagnosed as cirrhotic, the next AFP measurement should be performed **within 6 months of the previous test** unless clinically indicated sooner.
- If the patient did not have an AFP test within 6 months prior to being diagnosed as cirrhotic, they should undergo an AFP test **within 3 months** of diagnosis of cirrhosis.

Timing of subsequent AFP tests after a diagnosis of cirrhosis:

- The AFP test should be repeated **every 6 months from the previous test.**

14.4 DEFINITION OF END OF TRIAL

The end of the trial is defined as the date the last participant's last data item is collected..

14.5 CESSATION OF FOLLOW-UP

Cessation of follow-up should only occur under the following circumstances:

- Patient has completed the final follow-up visit at 30 months post-randomisation
- Patient undergoes liver transplantation
- Patient has an episode of severe encephalopathy of (Westhaven criteria 3-4) or otherwise loses capacity to consent
- Patient dies
- Patient withdraws from trial

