16 ECONOMIC EVALUATION

16.1 WITHIN-TRIAL ECONOMIC EVALUATION

The economic evaluation will compare the observed costs and outcomes of the cohort of patients randomised to ELF guided detection and management with those of a cohort of patients randomised to standard care. The perspective of the analysis will be that of the NHS and Personal Social Services.

The primary outcome measure for the within trial economic evaluation is the Quality Adjusted Life Years. Quality of Life weights will be calculated using the EQ-5D™ algorithm³⁷. Life years lived will be obtained from the mortality data collected within the clinical trial at the end of 30 months follow-up.

The primary analysis will consider all direct NHS and Social Care costs incurred by patients randomised to ELF guided detection and management or standard care. Health and social care resource utilisation will be identified using a simple questionnaire completed by the study participants at randomisation and follow-up visits.

Costs and outcomes will be discounted at 3.5% per annum. All costs will be indexed to the trial start year (2009) using the NHS Pay and Prices Index.

The primary result of the economic evaluation will be the incremental cost effectiveness ratio of ELF guided detection and management vs. standard care (ICER). This will be calculated as the difference in the mean cost of the interventions divided by the difference in the mean outcomes.

Parameter uncertainty will be examined using a non-parametric bootstrap simulation³⁸.

Results of the probabilistic sensitivity analysis will be presented as the expected incremental cost effectiveness ratio; a scatter plot on the cost effectiveness plane and as a cost effectiveness acceptability curve (CEAC). The Expected Net Benefit of ELF guided detection and management will be calculated for a range of values of lambda, including £5,000, £15,000, £20,000 and £30,000; reflecting the work of Martin and colleagues³⁹.

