17 ENDPOINTS

17.1 PRIMARY ENDPOINT

- Time from randomisation to occurrence of first severe complication

Severe complications are defined by:

1. Variceal haemorrhage confirmed by one of the following:
 - a) visualisation through endoscopy
 - b) imaging
 - c) post-mortem
2. Spontaneous bacterial peritonitis:
Ascites confirmed by:
 - a) Imaging and/or
 - b) aspiration*and* infection confirmed by:
 - a) microscopy and/or
 - b) culture
3. Hepatocellular cancer (HCC) beyond the Milan criteria^{* 40, 41}
N.B. For the purposes of the trial cases of HCC falling within the Milan criteria are not regarded as endpoints as they are regarded as treatable.
4. Encephalopathy - grade 3 or 4 defined using the Westhaven criteria (Appendix 1)⁴².
5. Liver-related mortality. Any of the following:
 - a) Any mention of liver disease in part one of the death certificate
 - b) death due to hepatocellular cancer (HCC)
 - c) death due to liver failure
 - d) death due to bleeding from portal hypertension
 - e) death due to hepato-renal syndrome
 - f) death due to sepsis occurring as a result of chronic liver disease
 - g) death due to spontaneous bacterial peritonitis
 - h) death due to encephalopathy

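### Sections 14.3 and 14.5 conflict on follow-up after grade 3-4 encephalopathy, and the within-trial costing states no source for terminal episodes or for costs once a transplant or such an episode ends visits

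*Protocol*

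**What the plan says.** **When follow-up stops.** Section 14.5 gives a closed list of reasons. Two of them are "Patient undergoes liver transplantation" and "Patient has an episode of severe encephalopathy of (Westhaven criteria 3-4) or otherwise loses capacity to consent"; death is another.

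**What happens after a complication.** Section 14.3 says that a patient may have "multiple episodes of liver related complications such as bacterial peritonitis, variceal haemorrhage or encephalopathy", sets no grade limit on encephalopathy, and then states: "Following on from a liver related complication, follow-up should continue on a 6-monthly schedule". It gives one exception: "If however, patients undergo liver transplantation, further 6 monthly follow-up will cease".

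**Where the event sits in the trial.** Section 17.1 makes it part of the primary endpoint: "Encephalopathy - grade 3 or 4 defined using the Westhaven criteria".

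**How costs are collected.** Section 16.1 sets the scope: "The primary analysis will consider all direct NHS and Social Care costs incurred by patients". It then names the source: "Health and social care resource utilisation will be identified using a simple questionnaire completed by the study participants at randomisation and follow-up visits". Section 16.2 repeats the evaluation with other quality-of-life weights and changes nothing else. Life years come from trial mortality data, not from visits.

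**What else is collected.** Sections 6.3 and 11 link every consenting patient to Hospital Episode Statistics and mortality records. The stated purposes are morbidity, mortality and endpoint data. Section 15.2.1 has encephalopathy and transplantation recorded on the CRFs. Section 16 names neither as a source of costs.

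**The concern.** There are two separate problems.

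First, a site that follows section 14.3 keeps seeing a patient after a grade 3-4 episode, and a site that follows section 14.5 stops. The same endpoint event would then leave different amounts of later data at different sites.

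Second, the only stated source of resource use is a form that the patient must be alive, and still attending, to complete. A patient who dies cannot report the final admission. A patient whose visits end at a transplant or a grade 3-4 episode completes no later form on which that admission or the care after it could be entered. EQ-5D values after cessation are lost as well, although survival continues to be counted.

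This loss is triggered by outcome. Aim (d) in section 5.1 asks whether ELF improves cost-effectiveness, and these are events that ELF is meant to prevent. The added endoscopy, ultrasound and AFP testing in the ELF arm is recorded in patients who stay in follow-up. The costs of events averted would be under-recorded, more so in the control arm if ELF works.

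**Working it through.** **The text.** The protocol states no figure on this point, so the first step is to set the sections side by side.

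| Event | 14.3 | 14.5 | Consistent? |
|---|---|---|---|
| Transplantation | visits cease | follow-up ceases | yes |
| Grade 3-4 encephalopathy | 6-monthly visits continue | follow-up ceases | no |
| Variceal haemorrhage, bacterial peritonitis | visits continue | not a reason to stop | yes |

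Section 14.5 is the more specific on grade, but that does not settle the conflict, because section 14.3 states its own exception and leaves encephalopathy out of it.

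**The number of patients.** Inputs, all from section 18.1:

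- About 700 randomised, so 350 per arm.
- 37% with ELF above 9.49. The count given is 80/225 = 35.6%, and 40% is used later in the same section, so the range is 35.6% to 40%.
- Control rates at 36 months in patients with ELF ≥9.5: 7.5% liver-related mortality, 1.5% transplantation, 10% decompensation, 3% variceal bleeds. These sum to the stated 22%, so the protocol itself adds them without overlap.
- An assumed 40% reduction in the ELF arm.

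Steps, with 30-month risk = 1 − (1 − p)^(30/36):

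1. Controls with ELF ≥9.5: 0.37 × 350 = 129.5.
2. Liver death: 1 − 0.925^(30/36) = 0.0629; × 129.5 = 8.1.
3. Transplantation: 1 − 0.985^(30/36) = 0.0125; × 129.5 = 1.6 (1.56 to 1.75 over the range of shares).
4. Control total: 9.8. ELF arm: 9.8 × 0.6 = 5.9. Difference: 3.9 patients.
5. Share of the control total that is deaths: 8.1/9.8 = 83%.
6. Encephalopathy: the protocol gives no rate. The decompensation rate gives an upper limit: 1 − 0.90^(30/36) = 0.0841; × 129.5 = 10.9 controls, if every decompensation were a grade 3-4 episode. The lower limit is none.

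**In money.** The protocol gives no unit costs. For each £1,000 left unrecorded per affected patient, deaths and transplants together understate the control mean by 9.8 × 1,000/350 = £28 and the ELF mean by 5.9 × 1,000/350 = £17. The saving is then understated by about £11 per randomised patient. Purely as an illustration, £10,000 to £60,000 per episode would give about £110 to £670, or 0.006 to 0.033 QALY at the £20,000 threshold in section 16.1. Transplants alone (difference 1.6 × 0.4 = 0.65 patients) would give about £19 to £111.

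**The case against.** A reader might infer that these costs are never counted. The documents do not support that. Hospital Episode Statistics linkage covers all consenting patients and does not stop under section 14.5, the CRFs record the events, and section 17.2 lists the economic evaluation among the secondary endpoints, so linked data could be used for it. The lifetime model in section 16.3 rests on an existing model whose parameters are not described, and no loss is shown there. What stands is narrower: section 16 fixes the questionnaire as the source and does not name linkage.

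A reader might also take the gap to cover all the worst outcomes. It does not. Non-fatal variceal haemorrhage, bacterial peritonitis and hepatocellular cancer beyond the Milan criteria do not end follow-up, so survivors with capacity go on completing forms. Nor is the primary analysis harmed: it is time to first severe complication, and a grade 3-4 episode is already such an event.

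Further points are fair. About 83% of the patients counted are deaths, and reconciling 14.3 with 14.5 recovers none of their costs; only a change of cost source does. Section 14.5 ties the encephalopathy rule to loss of capacity, and the questionnaires are self-completed, so the rule has an evident reason. Ending visits at transplantation is consistent in both sections and is a design choice, not an error. Later morbidity can come from linkage, and section 19.2.2 plans multiple imputation for quality of life.

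The strongest point concerns direction. The bias against ELF is conditional on ELF reducing these events within the trial horizon, and section 18.1 says that the major liver events need five further years. If the arms do not differ, both means are understated by similar amounts and the difference is little affected.

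The detail of costing may be left to an analysis plan. The choice of source is not such a detail, since the protocol has already fixed it, and no analysis can recover forms that were never completed.

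**Conclusion.** The point holds in two parts. Sections 14.3 and 14.5 contradict each other for grade 3-4 encephalopathy. Separately, the within-trial evaluation (16.1, carried into 16.2) promises all direct costs but states no source for terminal episodes, or for costs from a transplant or a grade 3-4 episode that ends follow-up.

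The size is modest: about 8 liver deaths and 1.6 transplants among 350 controls, about 6 such patients in the ELF arm if the 40% reduction occurs, and an unknown number of encephalopathy cases. This assumes that the section 18.1 rates hold, that all patients are observed for 30 months, and that events below ELF 9.5 are ignored. Any monetary figure rests on assumed unit costs. The direction, an understated saving from ELF, is conditional on ELF working. The cost-effectiveness aim is affected; the primary endpoint is not.

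**What to change.** 1. Reconcile sections 14.3 and 14.5 so that one rule governs follow-up after grade 3-4 encephalopathy. Which rule applies is for the trial team to decide.
2. State in section 16.1 that inpatient, transplant and terminal episodes are costed from the Hospital Episode Statistics linkage for every randomised patient, in both arms, from randomisation to death or 30 months. Section 16.2 then follows.
3. Keep the questionnaire for primary and social care, and resume it where the patient is able to complete it.

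New notes-based CRFs in patients who have lost capacity are not needed for this, and should not be added unless consent covers them.

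The cost is amendment wording and some extra costing work on linked records. The linkage is already consented and planned. Since section 8.2 describes it as serving morbidity and mortality relating to the endpoints, the data request should name costing as a use.

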14.6 PREGNANCIES

All pregnancies and suspected pregnancies must be reported immediately to the CTRU Trial Manager/Coordinator. If pregnancy is confirmed, patients should continue follow-up assessment if possible, however, no trial-specific interventions (i.e. ELF testing) should be performed.

14.7 QUALITATIVE SUB-STUDY

Patient understandings of clinical biomarkers and experiences of testing, their acceptability to the patients, their perceived utility and patient experiences and motivations for testing are important factors of translation of biomarkers into clinical practices. As such, qualitative research will be performed in a small sample of participants in this study, consisting of in-depth semi-structured interviews which will last on average of an hour. This qualitative work will form a separate protocol and will obtain separate ethical approval to the main trial.

15 SERIOUS ADVERSE EVENTS PROCEDURES

15.1 GENERAL DEFINITIONS

An adverse event (AE) is any untoward medical occurrence in a patient or clinical trial subject which does not necessarily have a causal relationship with this trial intervention and can include;

- any unintentional, unfavourable clinical sign or symptom
- any new illness or disease or the deterioration of existing disease or illness
- any clinically relevant deterioration in any laboratory assessments or clinical tests.

In addition the following criteria may be used in order to collect protocol-defined reportable adverse events which do not meet the criteria for serious (below):

- requires medical or surgical intervention to prevent permanent impairment of function or permanent damage to body structure.

A Serious Adverse Event (SAE) is defined in general as “any untoward medical occurrence or effect that:

- results in death,
- is life-threatening*,
- requires inpatient hospitalisation or prolongation of existing hospitalisation,
- results in persistent or significant disability or incapacity,
- consists of a congenital anomaly or birth defect,
- may jeopardise the patient and may require medical or surgical intervention to prevent one of the outcomes listed above.

*the term life-threatening refers to an event in which the patient was at risk of death at the time of the event; it does not refer to an event which hypothetically might have caused death if it was more severe.

A SAE occurring to a research participant, where in the opinion of the Chief Investigator the event is Related and Unexpected will be reported to the main Research Ethics Committee (REC). The National Research Ethics Service (NRES) defines Related and Unexpected SAEs (RUSAEs) as follows:

- *Related*: that is, it resulted from administration of any research procedures; and
- *Unexpected*: that is, the type of event is not listed in the protocol as an expected occurrence.

15.2 STUDY DEFINITIONS

15.2.1 Expected AE/SAEs – Not Reportable

This is a trial investigating ELF as a monitoring tool in a patient population with high levels of morbidity and co-morbid diseases and as such in this patient population, acute illness resulting in hospitalisation, new medical problems and deterioration of existing medical problems are expected.

For the purposes of this trial, adverse events related to the underlying disease under study or treatment for disease under study will be collected and recorded in the CRFs and followed as appropriate. These adverse events may include (but does not represent an exhaustive list):

- Varices with or without bleeding
- Ascites
- Spontaneous Bacterial Peritonitis
- Encephalopathy
- Liver cancer
- Alcohol injection of liver tumour
- Embolisation of liver tumour
- Chemo-embolisation of liver tumour
- Radiofrequency ablation of liver tumour
- Transplantation
- Cirrhosis
- Venepuncture injury (in ELF monitoring arm)

- Oesophogastroduodenoscopy complications (ruptured varices, perforated oesophagus)
- Complications of treatment for portal hypertension (requiring intervention including bradycardia, cardiac arrest, collapse related to beta blocker treatment)
- Complications of management of HCC (imaging adverse events e.g. contract reaction)

In recognition of this, events fulfilling the definition of an adverse event or serious adverse events will not be reportable in this study unless they are classified as 'related' to trial procedures.

15.2.2 Related and Unexpected SAEs – Expedited Reporting

All Related and Unexpected SAEs occurring from the date of consent up to 30 months post randomisation must be recorded on the Related & Unexpected Serious Adverse Event Form and faxed to the CTRU within 24 hours of the trial team becoming aware of the event. The original form should also be posted to the CTRU in real time and a copy retained on site.

For each study Related & Unexpected SAE the following information will be collected:

- full details in medical terms with a diagnosis, if possible
- its duration (start and end dates if applicable)
- action taken
- outcome
- causality (i.e. relatedness to investigation), in the opinion of the investigator
- whether the event would be considered expected or unexpected

Any follow-up information should be faxed to the CTRU as soon as it is available. Events will be followed up until the event has resolved or a final outcome has been reached. All Related & Unexpected SAEs will be reviewed by the Chief Investigator and subject to expedited reporting to the Sponsor and the main REC by the CTRU on behalf of the Chief Investigator within 15 days.

15.3 RESPONSIBILITIES

15.3.1 Principal Investigator/Authorised Individual at local site

- 1) Checking for SAEs when patients attend for treatment/follow-up
- 2) Judgement in assessing:
 - Seriousness
 - Causality
 - Expectedness
- 3) To ensure all Related & Unexpected SAEs are recorded and reported to the CTRU within 24 hours of becoming aware and to provide further follow-up information as soon as available
- 4) To report Related & Unexpected SAEs to local committees in line with local arrangements.

15.3.2 Chief Investigator

- 1) Assign relatedness and expected nature of SAEs where it has not been possible to obtain local assessment
- 2) Undertake SAE review
- 3) Review all events assessed as Related & Unexpected in the opinion of the local investigator. In the event of disagreement between the local assessment and the Chief Investigator or Co-Chief Investigators, local assessment may be upgraded or downgraded by the Chief Investigator prior to reporting to the main REC.
- 4) Review annual/periodic safety reports as required.

15.3.3 CTRU

- 1) Expedited reporting of Related & Unexpected SAEs to the main REC and Sponsor within required timelines
- 2) Preparing annual safety reports to the main REC and periodic safety reports to the Project Team.
- 3) Notifying Investigators of Related & Unexpected SAEs which compromise patient safety.

